2.2.3 Care of Supplies

All supplies used in the study must be maintained securely under the direct responsibility of the Chief Investigator or under that delegated by the Investigator.

All supplies shall be dispensed in accordance with the Investigator's direction and it is the Investigator's responsibility to ensure an accurate record of supplies issued and returned is maintained.

All supplies should be stored at room temperature, out of direct sunlight, and protected from extremes of environmental conditions.

All supplies will be used only while participating in the study and returned to MEC at the end of the study for weighing before being returned to Alliance Pharmaceuticals Ltd.

2.2.4 Study Materials

Alliance Pharmaceuticals Ltd. will supply all the clinical study materials required for the duration of the study. In addition, numbered CRFs, patient diaries and other documentation will be prepared for each participant on behalf of the Sponsor by the Clinical Research Organisation or Insect Research and Development Limited.

2.2.5 Compliance

All supplies used, partly used, or unused will be maintained for collection by the investigators.

2.3 Procedures and Investigations

2.3.1 Treatment Regimen/Allocation

This is a randomised, double-blinded, parallel group study of Vamousse Lice Defence Shampoo and The Control Shampoo in the prevention of the spread of head louse infestation. Each household which satisfies the inclusion/exclusion criteria will be randomised into one of two equal sized study arms, stratified by family size. As there may be households where the index case is not the only overt infestation on Day 0, the population will also be stratified on this criterion (overt infestation on Day 0 = 1 or >1). Following treatment of the index case, participants in one arm will be treated with Vamousse Lice Defence Shampoo and in the second arm with The Control Shampoo. Anyone found to be infested at the end of the study (Day 14) will be treated using the standard of care product (Vamousse Treatment Mousse).

2.3.2 Randomisation

The randomised treatment allocation code will be generated using the free online randomisation service provided at http://www.randomization.com/. The treatment allocation will be made in 22 balanced blocks of 8 treatments, which will provide sufficient numbers for the randomisation allocations together with enough additional allocations as may be required to address any overruns or replacements. The Seed number and date of randomisation will be recorded on the randomisation plan. The randomisation sequence will be held by the packaging company responsible for clinical trial supply and, in order to maintain blinding, will not be revealed to the sponsor, investigators or other study personnel until the end of the study.

The individual treatment allocations will be prepared as sheets bearing the anonymous identification of the product to be used (bottle number) and instructions for application. The product identification/instruction sheets will be sealed in opaque envelopes numbered sequentially on the outside with the participant number taken from the randomisation schedule. Each envelope will be enclosed in a CRF prior to use. Each investigator delegated to enrol participants will allocate the numbered CRFs to participants in numerical sequence. However, where two or more investigators, each allocated separate blocks of numbers, enrol participants in parallel the overall chronological sequence will not necessarily follow the numerical sequence.

Only after written informed consent has been obtained will the investigator allocate a study number and open the randomisation envelope for that number. As detailed above, the envelopes will contain no other information that could compromise blinding. The investigating team will keep a copy of the randomisation code also in a sealed envelope, in case an adverse event, reaction, or any other emergency circumstance necessitates that the code be broken.

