2.3.3.2 Recruitment (Day 0)

Screening:

Each potential index case will be asked for permission to assess their hair to determine

whether live head lice are present at the start of the study. The assessment will be made by dry combing the hair with a plastic fine-toothed head louse detection comb. Any family member complaining of symptoms of infestation will also be assessed and if confirmed, will be recorded in the CRF. Thereafter, they will receive treatment as though they are an index case. Other family members will not be assessed.

Details will be recorded of how many people share the place of residence with the index case(s).

Consent/Assent:

Potential participants and/or parents/guardians will be asked if they understand the requirements of the study, as set out in the PIB, and if they have any further questions concerning it. Provided they still wish to enter the study and meet the inclusion/exclusion criteria for entry, the participant or parent/guardian (when the participant is below the age of 16) will read and sign the Consent Form. The Investigator will countersign the Consent Form.

A separate Assent Form will be available for those under the age of 16 provided they are capable of signing their name. The Investigator and the parent/guardian will countersign the Assent Forms. A copy of the Consent Form and, if appropriate the Assent Form, will be given to the individual or the carer.

Should an adult member of the household not meet with the inclusion/exclusion criteria, it may not necessarily mean the entire household is ineligible. At the discretion of the investigator, the household may be enrolled and the excluded family member will recorded as a non-participant.

Case Record Form completion:

Personal data allowing identification of an individual will not be recorded in the CRF. However, as there are no source medical documents (i.e. patient medical records) available to the investigators, a Source Data Verification Sheet will be completed for each participant that will be maintained separately from all other study documentation. This Sheet will include information such as name, date of birth, address, and contact details for the General Practitioner. A copy of the GDPR statement covering security of personal data collected during the course of the study will be given to the carer.

The following information will be recorded in the CRF:

- 1. Declaration of Receipt of Informed Consent and GDPR statement:

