 - Confirmation that informed consent and assent (where relevant) was obtained by the investigator, that a copy of the consent has been given to the participant and/or parent guardian, and that the original will be retained. Confirmation that the participant was in receipt of the GDPR statement outlining their rights with respect to personal data held as a result of participation in the study.
- 2. **Identification**: Participant's study number, gender, age.
- 3. Hair Characteristics: Characteristics will be recorded of the participant's hair:
 - a) Length: closely cropped, above ears, ears to shoulders, below shoulders
 - b) Thickness: fine, medium, thick
 - c) Degree of curl: straight, wavy, curly
 - d) Type: dry, normal, greasy
- 4. **Head Lice Details**: The investigator will make a subjective assessment of the severity of the current louse infestation in the index case using the following scale:
 - a) Light infestation: lice only found after several combs of the hair
 - b) Moderate infestation: single louse found on the first comb of the hair
 - c) Heavy infestation: more than one louse found on the first comb of the hair
- 5. **Medication Current at Entry**: Any medication being taken along with the date the medication started the total dose and the reason for the medication.
- 6. **Medical History**: Medical history and any current illnesses will be recorded.
- 7. **Inclusion/Exclusion Criteria**: Confirmation that the participant meets the inclusion/exclusion criteria for entry into the study.

Procedure:

All Index Cases will be treated using Vamousse Treatment Mousse on Day 0. The product will be applied directly to dry hair. Sufficient product will be applied to saturate the hair and scalp. The product will be left in place for 15 minutes and then it will be washed off by rinsing with the treatment shampoo and water. Hair can be dried in the usual way following hair washing after treatment. Full instructions for use are provided.

All other participating household members will commence using the treatment shampoo on Day 0. The shampoo should be applied generously to wet hair, lathered and massaged into the scalp. It should then be left in the hair for at least 3 minutes but not more than 5 minutes before it is thoroughly rinsed out of the hair. The shampoo should be used once a day for the duration of the study.

The Investigator will issue participants with the patient diary and give them instruction in its use.

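### A single block size of 8, printed in the protocol and used in numerical order, makes the end of each block predictable if staff come to recognise the shampoos

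*Protocol*

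**What the plan says.** Section 2.3.2 of the protocol fixes the block structure: "The treatment allocation will be made in 22 balanced blocks of 8 treatments". Section 2.3.1 gives equal arms: each household "will be randomised into one of two equal sized study arms, stratified by family size". On order of use, 2.3.2 says: "Each investigator delegated to enrol participants will allocate the numbered CRFs to participants in numerical sequence". It allows for the case "where two or more investigators, each allocated separate blocks of numbers, enrol participants in parallel".

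The same section lists safeguards. The packaging company holds the sequence, which "will not be revealed to the sponsor, investigators or other study personnel until the end of the study". Envelopes are opaque and sealed, and: "Only after written informed consent has been obtained will the investigator allocate a study number and open the randomisation envelope for that number". Section 2.3.1 calls the study double-blinded, and section 2.2.2 gives both products the same pack type and individually numbered bottles.

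On the products themselves, section 2.2.1 lists tea tree oil, eucalyptus oil and a fragrance oil/geraniol entry at 1.865% for the test shampoo. For the control it lists litchi extract, parfum, coumarin, limonene and linalool. There is no statement about matching. On Day 0 the Mousse is "washed off by rinsing with the treatment shampoo and water" (section 2.3.3.2).

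On entry, section 2.3.3.2 leaves some room for judgement where an adult is ineligible: "At the discretion of the investigator, the household may be enrolled and the excluded family member will recorded as a non-participant".

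**The concern.** Sealed envelopes opened after consent stop an investigator from reading the next allocation. They do not stop anyone from inferring it from past allocations once the block size is known. With CRFs used in numerical order, block boundaries can be worked out as 8, 16, 24 and so on. The remaining protection is that nobody can tell earlier allocations apart, and the protocol does not describe how smell, colour or texture are masked.

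The team has repeated contact with treated hair. It applies the Mousse on Day 0, checks index cases on Day 3 and, if needed, Day 6, and combs every participant and collects leftover product at Day 14. Participants are told to avoid other hair products (section 2.3.4), so there is less to cover a scent. An observer need not know which shampoo is active: sorting households into two groups is enough to see which group is running short in a block.

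If the next allocation can be guessed, the choice of which household to enrol can follow it. Most household members are not examined for lice on Day 0 (sections 1.4 and 2.3.3.2), yet they count in the primary outcome, the proportion infested per household at Day 14 (section 3.1.2). Selection on their unrecorded status would feed into that comparison.

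**Working it through.** **Inputs.** 22 blocks of 8, balanced (2.3.2); 1:1 allocation (2.3.1); 84 households needed, 42 per arm (3.4). The recognition rate is not in the protocol and is varied below.

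**1. The plan's own figure.** 22 × 8 = 176 allocations against 84 needed, which take 84/8 = 10.5 blocks. The list is long enough, as 2.3.2 says.

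**2. If masking holds.** Past allocations carry no information, and the next one is guessed correctly 50% of the time whatever the block size.

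**3. Ceiling: every past allocation recognised, one person filling the block in order.** A 4:4 block has C(8,4) = 70 equally likely orderings. An allocation is certain once one arm has used its four places, so all remaining places belong to the other arm.

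| Position | Orderings in which it is certain | Probability | Best guess correct |
|---|---|---|---|
| 1 | 0 | 0 | 0.500 |
| 2 and 3 (each) | 0 | 0 | 0.571 |
| 4 | 0 | 0 | 0.629 |
| 5 | 2·C(4,4) = 2 | 2.9% | 0.629 |
| 6 | 2·C(5,4) = 10 | 14.3% | 0.714 |
| 7 | 2·C(6,4) = 30 | 42.9% | 0.714 |
| 8 | 70 | 100% | 1.000 |

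- Certain per block: (2 + 10 + 30 + 70)/70 = 112/70 = 1.6 of 8, or 20%.
- Correct guesses per block: 0.500 + 2(0.571) + 2(0.629) + 2(0.714) + 1.000 = 5.33 of 8, or 67%.

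**4. Over 84 households in one running sequence** (10 full blocks and half a block). Certain: 10 × 1.6 + 0 = 16, or 19%, because positions 1–4 are never certain. Correct guesses: 10 × 5.329 + (0.500 + 0.571 + 0.571 + 0.629) = 55.6, against 42 by chance.

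**5. Imperfect recognition.** Same 70 orderings, with each past allocation identified correctly with probability r and the guesser using that information as well as possible:

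| r | Best guess correct | Correct of 84 | Certain |
|---|---|---|---|
| 1.0 | 67% | about 56 | 16 |
| 0.9 | 60% | about 51 | 0 |
| 0.8 | 57% | about 48 | 0 |
| 0.7 | 54% | about 45 | 0 |
| 0.5 (masked) | 50% | 42 | 0 |

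**6. What varied block sizes would do.** Simulation of 84 allocations with perfect recognition, for a guesser who knows the set of possible sizes but not their order:

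| Block sizes | Certain | Best guess correct |
|---|---|---|
| 8 only | 19% | 66% |
| 4, 6, 8 at random | 2.4% | 68% |
| 8, 10, 12 at random | 1.3% | 65% |

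Varying the size removes nearly all the certainty and leaves the better-than-chance guessing almost unchanged.

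**The case against.** The strongest reply is that the protocol states double blinding, anonymous bottle numbers with no A/B code, the same pack, and opening only after consent. If that masking works, block size is irrelevant. This stands as far as it goes. A reader might infer from the ingredient lists that investigators can tell the shampoos apart. The protocol does not say so: different ingredients make recognition possible, not established, and the text does not say who rinses off the Mousse.

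A reader might also infer that whole randomisation blocks go to single investigators. The protocol speaks only of blocks of numbers, and only when two or more people enrol in parallel; it does not say that these are the blocks of 8. Split or unfinished blocks, across investigators or strata, would lower the figures.

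Nor would selection be invisible in general. Index-case severity and the number of people in the home are recorded on Day 0 (2.3.3.2). Number of children and number of overt infestations are strata in the primary analysis, and section 3.4 allows further stratified tests if baseline differences appear. What stays unmeasured is the lice status of the members who are not examined.

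Scope for choice is also limited. The suitability interview comes before the visit, the study number only after consent, and the discretion quoted covers only households with an ineligible adult.

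None of this answers the narrower point: a fixed, printed block size adds avoidable predictability where masking of scent and appearance is undescribed.

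**Conclusion.** The point holds as a conditional weakness with a cheap remedy. One disclosed block size of 8, used in numerical order, makes block ends predictable if earlier allocations are recognised. The size is at most 20% of allocations certain (about 16 of 84) and at most 67% guessed correctly. Both are ceilings that need error-free recognition and one person filling each block in order. At 70–90% recognition the guess is right 54–60% of the time with nothing certain, and with effective masking it is right 50% of the time.

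The documents do not support a statement that the primary comparison is biased. They show neither that the products are recognised nor that enrolment would follow a guess, and no effect on the Day 14 result can be calculated from them.

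**What to change.** In section 2.3.2, before envelopes are packed:

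- generate the list with randomly varied block sizes, held only by the packaging company;
- remove the block size from the protocol and from all site papers;
- when investigators enrol in parallel, give them runs of numbers that do not coincide with block boundaries.

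Under perfect recognition this reduces certain allocations from about 20% to about 1–2%. Best-guess success stays at about 65–68%, so the change does not cure doubtful masking. It would help to state in section 2.2 whether, and how, smell, colour and texture are matched or disguised.

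The cost is a new list and a short text change. The downside is a slightly larger possible imbalance when recruitment stops: half the largest block, for example 12/2 = 6 households in one sequence with blocks up to 12, against 8/2 = 4 now. Recruitment already continues until each arm has at least 42.

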2.3.3 Study Methodology

2.3.3.1 Pre-recruitment

Some participants may be obtained via schools and/or school nurses with whom MEC collaborates in screening for head louse infestation. Primarily recruitment will be via radio advertising. Respondents to advertising will be put in contact with MEC via a "text-back" service. When contact is made, a detailed Participant Information Booklet (PIB) will be provided by post or email to explain the purpose of the study. This will include a children's section explaining what will happen if the person enters the study. It will also contain a General Data Protection Regulation (GDPR) statement relating to protection of the integrity of personal data.

On first contact a member of the study team will conduct a brief interview to establish whether the person(s) will be suitable for entry into the study. If they wish to enter the study, they will be visited and conducted through a consent process, which includes explanation of study procedures and answers to any questions about the study. Potential participants must have had access to the PIB for at least 24 hours before the recruitment visit takes place.

2.3.3.2 Recruitment (Day 0)

Screening:

Each potential index case will be asked for permission to assess their hair to determine

whether live head lice are present at the start of the study. The assessment will be made by dry combing the hair with a plastic fine-toothed head louse detection comb. Any family member complaining of symptoms of infestation will also be assessed and if confirmed, will be recorded in the CRF. Thereafter, they will receive treatment as though they are an index case. Other family members will not be assessed.

Details will be recorded of how many people share the place of residence with the index case(s).

Consent/Assent:

Potential participants and/or parents/guardians will be asked if they understand the requirements of the study, as set out in the PIB, and if they have any further questions concerning it. Provided they still wish to enter the study and meet the inclusion/exclusion criteria for entry, the participant or parent/guardian (when the participant is below the age of 16) will read and sign the Consent Form. The Investigator will countersign the Consent Form.

A separate Assent Form will be available for those under the age of 16 provided they are capable of signing their name. The Investigator and the parent/guardian will countersign the Assent Forms. A copy of the Consent Form and, if appropriate the Assent Form, will be given to the individual or the carer.

Should an adult member of the household not meet with the inclusion/exclusion criteria, it may not necessarily mean the entire household is ineligible. At the discretion of the investigator, the household may be enrolled and the excluded family member will recorded as a non-participant.

Case Record Form completion:

Personal data allowing identification of an individual will not be recorded in the CRF. However, as there are no source medical documents (i.e. patient medical records) available to the investigators, a Source Data Verification Sheet will be completed for each participant that will be maintained separately from all other study documentation. This Sheet will include information such as name, date of birth, address, and contact details for the General Practitioner. A copy of the GDPR statement covering security of personal data collected during the course of the study will be given to the carer.

The following information will be recorded in the CRF:

- 1. Declaration of Receipt of Informed Consent and GDPR statement:
 - Confirmation that informed consent and assent (where relevant) was obtained by the investigator, that a copy of the consent has been given to the participant and/or parent guardian, and that the original will be retained. Confirmation that the participant was in receipt of the GDPR statement outlining their rights with respect to personal data held as a result of participation in the study.
- 2. **Identification**: Participant's study number, gender, age.
- 3. Hair Characteristics: Characteristics will be recorded of the participant's hair:
 - a) Length: closely cropped, above ears, ears to shoulders, below shoulders
 - b) Thickness: fine, medium, thick
 - c) Degree of curl: straight, wavy, curly
 - d) Type: dry, normal, greasy
- 4. **Head Lice Details**: The investigator will make a subjective assessment of the severity of the current louse infestation in the index case using the following scale:
 - a) Light infestation: lice only found after several combs of the hair
 - b) Moderate infestation: single louse found on the first comb of the hair
 - c) Heavy infestation: more than one louse found on the first comb of the hair
- 5. **Medication Current at Entry**: Any medication being taken along with the date the medication started the total dose and the reason for the medication.
- 6. **Medical History**: Medical history and any current illnesses will be recorded.
- 7. **Inclusion/Exclusion Criteria**: Confirmation that the participant meets the inclusion/exclusion criteria for entry into the study.

Procedure:

All Index Cases will be treated using Vamousse Treatment Mousse on Day 0. The product will be applied directly to dry hair. Sufficient product will be applied to saturate the hair and scalp. The product will be left in place for 15 minutes and then it will be washed off by rinsing with the treatment shampoo and water. Hair can be dried in the usual way following hair washing after treatment. Full instructions for use are provided.

All other participating household members will commence using the treatment shampoo on Day 0. The shampoo should be applied generously to wet hair, lathered and massaged into the scalp. It should then be left in the hair for at least 3 minutes but not more than 5 minutes before it is thoroughly rinsed out of the hair. The shampoo should be used once a day for the duration of the study.

The Investigator will issue participants with the patient diary and give them instruction in its use.

2.3.3.3 Follow up Assessments (Days 3 & 6 ±1 day)

Index cases will be assessed for continued active lice infestation on Day 3. If live lice are present, a second treatment with Vamousse Treatment Mousse will be applied. Those index cases with evidence of active infestation on Day 3, will be assessed again on Day 6 and treated again if the infestation is still active.

